9.0 TREATMENT/INTERVENTION PLAN

9.1. Study Treatment

The investigational agents to be used in this study are copanlisib and ibrutinib. Copanlisib is given intravenously on days 1, 8, and 15 of 28 day cycles. Ibrutinib is given orally every day on 28 days cycles. The maximum duration of treatment is 36 cycles not exceeding 36 months. Dose changes or interruptions are allowed per below guidelines and must be recorded appropriately.

Study personnel will maintain a log of all drugs supplied to the patient. Drug supplies for each patient will be inventoried and accounted for. Subjects will be given diary cards to complete for the ibrutinib taken at home. Subjects must bring the diary cards to the site on every visit so study site personnel can verify compliance.

9.1.1 Copanlisib administration:

Copanlisib is supplied as lyophilized preparation in a 6-mL injection vial. The total amount of copanlisib, BAY 80-6946, per vial is 60 mg. The solution for IV infusion is obtained after reconstitution of the lyophilisate with 0.9% sodium chloride solution. Please refer to the Pharmacy Instructions for detailed instructions for the reconstitution of the lyophilisate and for further dilution of the reconstituted solution. Study drug is administered in a normal saline solution, intravenously, over 1 h (or per MSK protocol). No intravenous glucose preparations should be administered on the days of infusion. Dosing is weekly for the first 3 weeks of a 28-day cycle (on Days 1, 8, and 15), followed by a 1-week break (i.e., no infusion on Day 22). Patients will be on 30 mg, 45 mg or 60 mg depending on their dose level.

Laboratory blood tests on day 1 of copanlisib treatment must follow the below criteria:

Table 9-1: Laboratory test criteria for Day 1 dose of subsequent cycles

Laboratory Test	Criteria for Day 1 dose (Cycle 2 and higher)
Glucose	< 160 mg/dL (fasting) or < 200 mg/dL (non-fasting)
Hemoglobin	$\geq 8 \text{ g/dL}$ ^a
ANC	$\geq 1 \times 10^9$
Platelets	$\geq 75 \times 10^9$ ^b

ANC = Absolute neutrophil count;

a: If hemoglobin is < 8 g/dL but $\geq 6 \text{ g/dL}$ on the day of planned study drug administration it is permissible to give the study drug dose as scheduled and transfuse within 48 hours after the dose, if the patient is hemodynamically stable and in opinion of investigator benefits outweigh risks. Rationale and treatment should be recorded in source document and eCRF.

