9.7. Dose Continuation, Modification and Interruption

Subjects will be evaluated for AEs at each visit with the NCI CTCAE v5.0 used as a guide for the grading of severity. Prior to completion of cycle 1 in both dose escalation or dose expansion phase, treatment with either ibrutinib, copanlisib or both may be interrupted for \leq 7 days for any reason and then resumed at the same dose. If patients take less than 2 infusions of copanlisib or less than 14 days of ibrutinib during the intended dose of cycle 1, they will be excluded from the DLT analysis and replaced. However if a patient takes less than 14 days of the intended dose of cycle 1 due to a DLT, they will be included in the DLT analysis and not replaced. After completion of cycle 1, study drugs (either ibrutinib, copanlisib) may be interrupted for \leq 28 days for any reason and then resumed at same or reduced dose. The investigator may remove any patient from study for any toxicity if the investigator believes it is in the best interest of the patient to discontinue study treatment.

Intrapatient dose reduction will not be allowed during cycle 1 unless a DLT has occurred and been counted. This is in order to accurately determine the safe and tolerable dose of copanlisib when used in combination with ibrutinib. Dose reductions may be made to ibrutinib and/or copanlisib during cycles 2 and beyond. If a toxicity can be ascribed to a specific study drug, then that drug may be dose modified while the non-offending drug may be maintained. Whether to dose modify ibrutinib or copanlisib is at the discretion of the treating physician.

If the patient experiences unacceptable toxicity that fails to resolve after a maximum dose delay of 28 consecutive days, then the patient should be discontinued from the study treatments. In cases of treatment delays from reactivation of CMV, treatment delays can be extended for up to 2 months. In exceptional situations, if the patient is clearly benefiting from the study treatment (i.e. stable disease or better) and in the opinion of the investigator no safety concerns are present, the patient may remain on the study treatment. Patients who discontinue from study for a study related adverse event or an abnormal laboratory value must be followed as described in Section 10.

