Each patient is allowed a maximum of two dose reduction of each study drug. Dose reduction of copanlisib or ibrutinib indicates treatment at the next lower dose of copanlisib or ibrutinib based on Table 9-6. If after treatment interruption, resolution of toxicity, and treatment resumption at same dose, the subject presents with the same toxicity at the same severity, then the next treatment re-

initiation must resume at the next lower dose level irrespective of duration. A patient must discontinue therapy if after therapy is resumed at a lower dose, the same toxicity recurs with the same or worse severity. Copanlisib and ibrutinib dose modification guidelines for specific toxicities are outlined in Table 9-7.

Table 9-6. Intrapatient dose reduction*

Drug	Maximum Dose Levels	Reduction Dose Level 1	Reduction Dose Level 2
Copanlisib	60 mg	45 mg	30 mg
Ibrutinib	560 mg daily	420 mg daily	280 mg daily

*Dose reduction starts from the treating dose.

Dose escalation is allowed after the DLT period for ibrutinib to the FDA approved dose levels of 560 mg. However, patients will only be allowed to escalate to this dose once the DLT evaluation period for Dose Level 1 has passed and the dose will not exceed what has been deemed the MTD in other patients. There will be no intrapatient dose escalation of copanlisib. Once a dose reduction for copanlisib of a patient has occurred, the dose level may not be re-escalated during subsequent treatment cycles.

The sections below describe dose reduction steps for patients enrolled in the expansion phase of the study. For patients in the dose expansion phase, the dose must be held per these guidelines and these dose reduction steps can be followed after cycle 1 and per discussion with the PI. Inability to meet treatment criteria will result in holding the dose. If patients have been dose reduced to dose level -1 and continue to meet dose modification criteria to reduce the dose, they will be removed from study treatment.

Table 9-7. Dose modification guidelines

Toxicity Category	Severity (CTCAE 5.0 Grade)	Dose Modifications for ibrutinib	Dose Modifications for copanlisib
HEMATOLOGIC			

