			week), (or as per local practice) until return to within normal limits. Consider a bronchoscopy with biopsy and / or BAL.
	Grade \geq 3		Discontinue copanlisib
GASTROINTESTINAL	May dose modify/hold either ibrutinib, copanlisib or both as clinically indicated		
(*for patients with Gilbert Syndrome these dose modifications apply to changes in direct bilirubin only, Bilirubin will be fractionated if elevated)	Grade 1 ($>$ ULN - 1.5 \times ULN)	Maintain ibrutinib dose per investigator discretion	Maintain copanlisib dose level with LFTs* monitored as per protocol
	Grade 2 ($>$ 1.5 - 3.0 \times ULN) with ALT or AST \leq 3.0 \times ULN	Dose adjustments of ibrutinib per investigator discretion	Omit dose until resolves to \leq Grade 1, then: If resolved \leq 7 days, then maintain dose level If resolved $>$ 7 days, then reduce 1 dose level
	Grade 3 ($>$ 3.0 - 10.0 \times ULN) with ALT or AST \leq 3.0 \times ULN		Omit dose until resolves to \leq Grade 1, then: If resolved \leq 7 days, then maintain dose level If resolved $>$ 7 days, then discontinue
	Grade 4 ($>$ 10.0 \times ULN)	Discontinue ibrutinib	Discontinue copanlisib
Note: confounding factors and/or alternative causes for increased transaminases like concomitant medications, infection, hepato-biliary disorder, obstruction, liver metastasis, etc. should be excluded before dose interruption/reduction	Grade 1 ($>$ ULN - 3.0 \times ULN)	Maintain ibrutinib dose per investigator discretion	Maintain dose level with LFTs monitored as per protocol
	Grade 2 ($>$ 3.0 - 5.0 \times ULN) without total bilirubin elevation to $>$ 2.0 \times ULN	Dose adjustments of ibrutinib per investigator discretion	Maintain dose or reduce 1 dose level of copanlisib.
	Grade 3 ($>$ 5.0 - 20.0 \times ULN) without total bilirubin elevation to $>$ 2.0 \times ULN		Omit dose until resolves to \leq Grade 1, then reduce 1 dose level. If no recovery in \leq 28 days discontinue copanlisib, patient off study
	Grade 4 ($>$ 20.0 \times ULN) without bilirubin elevation to $>$ 2.0 \times ULN	Discontinue ibrutinib	Discontinue copanlisib

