AST or ALT Elevation and concurrent bilirubin elevation	AST or ALT $>$ 3.0 \times ULN and total bilirubin $>$ 2.0 \times ULN	Discontinue ibrutinib *** All patients with ALT or AST $>$ 3.0 \times ULN and total bilirubin $>$ 2.0 \times ULN in the absence of cholestasis ULN must immediately be withdrawn from copanlisib and every attempt should be made to carry out the liver event follow-up assessments	Discontinue copanlisib
Pancreatitis	Grade 2 (enzyme elevation or radiographic findings)	Dose adjustments of ibrutinib per investigator discretion	Dose adjustments of copanlisib per investigator discretion
	Grade 3 (medical intervention indicated)	Discontinue ibrutinib	Discontinue copanlisib

*** Hepatic toxicity monitoring (*for patients with Gilbert Syndrome: total and direct bilirubin must be monitored, intensified monitoring applies to changes in direct bilirubin only; the monitoring includes the following LFTs: albumin, ALT, AST, total bilirubin (fractionated if total bilirubin $> 2.0 \times \text{ULN}$), alkaline phosphatase (fractionated if alkaline phosphatase is grade 2 or higher) and GGT):

In case of any occurrence of ALT/AST, or bilirubin* increase \geq grade 2 the liver function tests must be monitored weekly or more frequently if clinically indicated until resolved to \leq grade 1

In case of any occurrence of ALT/AST, or bilirubin* increase \geq grade 3 the liver function tests must be monitored weekly or more frequently if clinically indicated until resolved to \leq grade 1; hereafter the monitoring should be continued every other week or more frequently if clinically indicated until the end of treatment with study medication

Patients who discontinued study treatment should be monitored weekly, including LFTs* or more frequently if clinically indicated until resolved to \leq grade 1 or stabilization (no CTCAE grade change over 4 weeks).

ENDOCRINE

Dose modify/hold copanlisib because of association with hyperglycemia. May dose modify/hold ibrutinib as clinically indicated			
Hyperglycemia	Level 1: Fasting glucose $> 125 - 160 \text{ mg/dL}$		Maintain copanlisib dose level

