
Note: The investigator may remove any patient from the study for any toxicity, if investigator believes that it is in the best interest of the patient.
 
Note: The investigator may dose reduce either ibrutinib or copanlisib. In situations where toxicities are associated with one drug, the investigator must hold and reduce drug associated with toxicity. The second drug may be continued or modified at the investigator's discretion.
 
Note: If any one drug is permanently discontinued, the patient will be taken off study unless in exceptional situations i.e. if the patient is clearly benefiting from the study treatment (i.e. stable disease or better) and in the opinion of the investigator no safety concerns are present, the patient may remain on the study treatment.
			

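### Table 9-7 drops the required copanlisib hold for bilirubin >1.5–2.0 x ULN when transaminases also rise to >3–5 x ULN

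*Combined protocol and SAP*

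**What the plan says.** The liver part of Table 9-7 in Section 9.7 has three groups of rows. The copanlisib instructions that matter here are these.

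- **Bilirubin Grade 2 (>1.5–3.0 x ULN) and Grade 3 (>3.0–10.0 x ULN).** Copanlisib is withheld until Grade 1 or lower. Both rows carry the condition "with ALT or AST \leq 3.0 \times ULN".
- **Transaminases Grade 2 (>3.0–5.0 x ULN).** The instruction is "Maintain dose or reduce 1 dose level of copanlisib". At Grade 3 (>5.0–20.0 x ULN) copanlisib is omitted and then reduced, and at Grade 4 it is discontinued. These rows apply "without total bilirubin elevation to" more than 2.0 x ULN.
- **"AST or ALT Elevation and concurrent bilirubin elevation".** AST or ALT >3.0 x ULN together with total bilirubin >2.0 x ULN means both drugs are discontinued.

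On the force of the table, Section 9.7 says that for expansion-phase patients "the dose must be held per these guidelines".

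**The concern.** The enzyme condition on the bilirubin rows appears meant to pass patients with a combined rise to the stricter combined-elevation row. The cut-offs do not meet, however. The bilirubin hold starts above 1.5 x ULN and the combined-elevation row starts above 2.0 x ULN. A patient between those limits whose enzymes pass 3 x ULN loses the hold before reaching the stricter row.

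This is a liver safety rule, and adding a second abnormal marker should not relax it. Except in patients with Gilbert's syndrome, the profile is outside the Section 6.2 entry limits even with liver involvement (bilirubin at most 1.5 x ULN, ALT/AST at most 3 x ULN), so it represents worsening on treatment. It also lies just below the protocol's own threshold for stopping both drugs.

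**Working it through.** No sample-size or error-rate arithmetic applies. The check is to read the rows as a decision table and see which ones apply to a given profile.

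**Inputs (Table 9-7, all x ULN).** Let B be bilirubin and M the higher of ALT and AST.

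- Bilirubin Grade 2: 1.5 < B ≤ 3.0, plus the enzyme condition: omit.
- Bilirubin Grade 3: 3.0 < B ≤ 10.0, plus the enzyme condition: omit.
- Transaminase Grade 2: 3 < M ≤ 5 and B ≤ 2.0: maintain or reduce.
- Transaminase Grade 3: 5 < M ≤ 20 and B ≤ 2.0: omit, then reduce.
- Transaminase Grade 4: M > 20 and B ≤ 2.0: discontinue.
- Combined elevation: M > 3 and B > 2.0: discontinue both drugs.

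The enzyme condition can be read as either enzyme at most 3 (literal) or both at most 3.

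**Step 1: profiles with ALT equal to AST, where the two readings agree.**

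| Bilirubin | ALT and AST | Row that governs copanlisib | Action |
|---|---|---|---|
| 1.8 | 1 | Bilirubin Grade 2 | Omit |
| 1.8 | 4 | Transaminase Grade 2 only | Maintain or reduce |
| 1.8 | 6 | Transaminase Grade 3 | Omit, then reduce |
| 1.8 | 21 | Transaminase Grade 4 | Discontinue |
| 2.1 | 4 | Combined elevation | Discontinue |

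At bilirubin 1.8 the instruction loosens and then tightens as enzymes rise.

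**Step 2: one enzyme raised (bilirubin 1.8, ALT 4, AST 2).** If both enzymes must be at most 3, the bilirubin row drops out and only maintain-or-reduce remains. On the literal reading, the bilirubin row (omit) and the transaminase row (maintain or reduce) both apply. They conflict, and the table does not say which takes precedence.

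**Step 3: extent of the gap.** The grid used bilirubin in steps of 0.1, and ALT and AST in steps of 0.5 up to 10 and then steps of 1 to 25. I counted profiles with no required hold although a milder profile has one.

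- Bilirubin values in the gap: 1.6 to 2.0, which is 5.
- Literal reading, both enzymes 3.5 to 5.0 (4 values each): 5 x 4 x 4 = 80 cells.
- Both-at-most-3 reading, higher enzyme 3.5 to 5.0: of 10 x 10 enzyme pairs up to 5.0, 6 x 6 have both at most 3.0, so 5 x (100 − 36) = 320 cells.

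The counts locate the gap. They are not patient frequencies.

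**Step 4: does another rule restore the hold?**

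- Table 9-1 in Section 9.1.1, "Laboratory test criteria for Day 1 dose of subsequent cycles", lists glucose, hemoglobin, ANC and platelets. It has no liver criterion.
- The heading over the liver block and the interruption allowances in Section 9.7 (up to 7 days in cycle 1, up to 28 days later) permit a hold but do not require one.
- The weekly liver tests required from Grade 2 upwards are monitoring only.
- In cycle 1 the reduction option is also closed: "Intrapatient dose reduction will not be allowed during cycle 1 unless a DLT has occurred and been counted". The row then offers only maintain, although a discretionary interruption remains possible.

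**The case against.** The strongest counter-argument is a note at the end of Table 9-7: "In situations where toxicities are associated with one drug, the investigator must hold and reduce drug associated with toxicity". If the liver change is attributed to copanlisib alone, this requires a hold, and it can be squared with the row's option to reduce. That stands as far as it goes. It does not help when attribution is shared or unclear, which is a real possibility with two drugs given together. Where it does apply, it contradicts the row's option to maintain the dose.

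Other points stand and limit the size of the problem:

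- On the literal reading, a patient with one enzyme at most 3 x ULN still meets the bilirubin hold, so the clean gap needs both enzymes >3–5.
- The row is weaker on the hold but not necessarily on later dose. The bilirubin row resumes the same dose if recovery takes 7 days or less, whereas the transaminase row allows an immediate reduction, and copanlisib reductions may not be reversed.
- A patient who worsens to bilirubin >2.0 or an enzyme >5 x ULN meets a mandatory rule, and weekly testing should show it soon. Three infusions in a cycle is therefore an upper limit that needs the patient to stay in the band.
- The investigator may always hold, and at most 45 patients will be treated across both phases.

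None of this supplies a required hold for the stable patient in the gap, and no stated rationale explains why the rule should loosen there.

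**Conclusion.** The concern holds. For bilirubin >1.5–2.0 x ULN with both enzymes >3–5 x ULN, Table 9-7 itself requires no copanlisib hold under either reading of the enzyme condition, while the same bilirubin with normal enzymes does require one. If the condition means both enzymes at most 3, one raised enzyme is enough.

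In the gap, up to three infusions per 28-day cycle (days 1, 8 and 15) may go ahead at full or one-level-lower dose, against none until Grade 1 under the bilirubin row. Continued dosing is allowed, not forced. The documents give no incidence for this profile, so I estimate no patient count, and it may be small. The primary endpoint and the Simon design are not affected.

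The conclusion rests on identifying the bilirubin and transaminase rows from their cut-offs and accompanying notes. For patients with Gilbert's syndrome, the bilirubin rows use direct bilirubin. The table should be corrected because the rule, if followed as written, gives a worse result for the sicker patient.

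**What to change.** Amend Table 9-7 in two places:

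1. Make the bilirubin Grade 2 and Grade 3 rows apply to every patient in those bilirubin bands who does not meet the combined-elevation row (AST or ALT >3.0 x ULN and total bilirubin >2.0 x ULN).
2. State that when more than one liver row applies, the most restrictive governs.

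For bilirubin >1.5–2.0 x ULN the copanlisib action then never weakens as enzymes rise: omit (up to 3), omit (>3–5), omit (>5–20), discontinue (>20). On the same grid the gap falls from 80 or 320 cells to 0 under either reading. The overlap between the bilirubin rows and the combined-elevation row, which the literal reading creates, also disappears.

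The same amendment could state whether the combined-elevation row uses direct bilirubin in Gilbert's syndrome, since Section 6.2 admits these patients with total bilirubin up to 3 x ULN. That is a clarification and carries no weight in the conclusion.

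The cost is a wording change to one table, with no added tests. The downside is a few more copanlisib holds.

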	
Level 4: > 500 mg/dL (≥ 27.8 mmol/L)
	
Dose adjustments of ibrutinib per investigator discretion
	
Immediately omit copanlisib, initiate or intensify medication with appropriate anti-diabetic treatment, re-check within 24 hours. If level improves then follow specific level recommendations.
 
If FPG is confirmed at Level 4:
 
• Administer intravenous hydration and intervention for electrolyte/ ketoacidosis/hyperosmolar disturbances as clinically appropriate• Discontinue patient from study• Instruct patient to follow dietary guidelines according to local and/or institutional standards for management of diabetes mellitus (such as those provided by the American Diabetes Association) during the study• Consider use of oral anti-hyperglycemic therapy such as metformin• Consider referral to endocrinologist for diabetic management 
For non-fasting plasma glucose >500 mg/dL (> 27.8 mmol/L) accompanied by signs/symptoms of hyperglycemia (for example, mental status changes, excessive thirst, polyuria), or presence of blood or urine

			ketones, discontinue copanlisib and following guidance for management of Level 4 fasting plasma glucose (FPG).
CARDIAC			
Arterial hypertension	Dose modify/hold copanlisib because of association with arterial hypertension. May dose modify/hold ibrutinib as clinically indicated		
	Pre-dose measurements BP \geq 150/90 mmHg	Maintain ibrutinib dose per investigator discretion	Delay copanlisib until recovery to < 150/90 mmHg Consider BP lowering medication. Dosing can proceed on the scheduled day if after at least 2 consecutive measurements BP returns to < 150/90 mmHg. If BP doesn't return to < 150/90 mmHg, delay dosing until next visit.
	During infusion: Grade 3 (\geq 160/100 mmHg)	Dose adjustments of ibrutinib per investigator discretion	Infusion can be interrupted or slowed down and administration of BP lowering therapy should be initiated. Infusion maybe resumed when BP has returned to < 150/90 mmHg at the investigator's discretion or skipped. Subsequent study drug administrations maybe reduced by 1 dose level at the investigator's discretion.

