	Post-dose: Drug-related Grade 3 (\geq 160/100 mmHg despite optimal anti-hypertensive treatment)	Dose adjustments of ibrutinib per investigator discretion	Administration of BP lowering therapy should be initiated according to local standard of care. Additional measurements to be performed as clinically indicated until recovery to < 150/90 mmHg. Subsequent study drug administrations maybe reduced by 1 dose level at the investigator's discretion.
Left ventricular systolic dysfunction *Event is considered resolved when the patient is asymptomatic, has a resting ejection fraction \geq 40% and \leq 20% decrease from baseline.	Dose modify/hold copanlisib because of association with cardiac dysfunction. May dose modify/hold ibrutinib as clinically indicated		
	Asymptomatic, resting ejection fraction 40-50%; or 10-20% drop from baseline	Maintain ibrutinib dose per investigator discretion	Maintain copanlisib dose level, and continue with caution Repeat LVEF within 4 weeks or as clinically appropriate
	Symptomatic, responsive to intervention, ejection fraction 20-39% or > 20% drop from baseline	Dose adjustments of ibrutinib per investigator discretion	- Omit copanlisib dose until resolved* (as defined to left), then reduce 1 dose level copanlisib - LVEF measurement to be repeated, if not resolved* within 28 days, permanently discontinue patient from copanlisib treatment
QTc prolongation	Refractory or poorly controlled, ejection fraction < 20%	Discontinue therapy	Discontinue therapy
	Dose modify/hold copanlisib because of association with QTc prolongation. May dose modify/hold ibrutinib as clinically indicated		
	QTc > 500 ms (\geq Grade 3) or > 60 ms change from baseline on at least two separate ECGs	Dose adjustments of ibrutinib per investigator discretion	First Occurrence: - Omit copanlisib dose

			
 - Perform a repeat ECG within one hour of the first QTc of > 500 ms or >60 ms from baseline. Repeat as clinically indicated until QTcF returns to < 480 ms - Seek cardiology input; address electrolytes, correct with supplements as clinically indicated ; review concomitant medication - Once QTc prolongation has resolved, restarted at one lower dose level 
Second Occurrence:
 
 - Off study
Dose modify/hold ibrutinib because of association with atrial fibrillation. May dose modify/hold copanlisib as clinically indicated			

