Grade 1	CT scans with lung windows. Repeat at least every 8 weeks (+/- 1 week), (or as per local practice) until return to within normal limits.	No specific therapy is required	No change	NA
Grade 2	CT scan with lung windows. Consider pulmonary function testing includes: spirometry, DLCO, and room air O ₂ saturation at rest. Repeat at least every 8 weeks (+/- 1 week), (or as per local practice) until return to within normal limits. Consider a bronchoscopy with biopsy and / or BAL.	Symptomatic only. Consider corticosteroids if symptoms are troublesome.	Dose interruption until recovery to ≤ grade 1	Decrease dose to the next lowest dose level, minimum dose is 30mg copanlisib ^a
Grade 3	CT scan with lung windows and pulmonary function testing includes: spirometry, DLCO, and room air O ₂ saturation at rest. Repeat at least every 8 weeks (+/- 1 week), (or as per local practice) until return to within normal limits. Bronchoscopy with biopsy and / or BAL is recommended.	Consider corticosteroids if infective origin is ruled out. Taper as medically indicated.	Discontinue copanlisib	NA
Grade 4	CT scan with lung windows and required pulmonary function testing, if possible, includes: spirometry, DLCO, and room air O ₂ saturation at rest. Repeat at least every 8 weeks (+/- 1 week), (or as per local practice) until return to within normal limits. Bronchoscopy with biopsy and / or BAL is recommended if possible.	Consider corticosteroids if infective origin is ruled out. Taper as medically indicated.	Discontinue copanlisib	NA

Guidelines for the treatment of copanlisib induced arterial hypertension

No dose should be given if blood pressure is ≥ 150/90 mmHg. Antihypertensive medication may be given to control the increased blood pressure. Dosing can proceed on the scheduled day if there are at least 2 consecutive measurements <150/90 mmHg. Otherwise dosing must be delayed.

If drug-related arterial hypertension (post-dose blood pressure of CTCAE Grade 3 or \geq 160/100 mmHg) is not manageable with optimal antihypertensive treatment, the dose for the subsequent copanlisib administrations may be reduced by 1 or 2 dose levels at the investigator's discretion. Patients with a post-dose blood pressure that may have life-threatening consequences (e.g. malignant arterial hypertension, transient or permanent neurologic deficit, hypertensive crisis) must permanently discontinue the study drug. Please see table 9-7.

Treatment of blood pressure increases associated with copanlisib

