It is important that patients with pre-existing arterial hypertension adhere to their regular medication schedule and take their usual doses on the days of study drug infusion.

The management of acute blood pressure increases following copanlisib will need to be individualized for each patient, but experience in Phase I has suggested the benefit of dihydropyridine calcium channel blockers (i.e. amlodipine, felodipine). Topical nitrates should also be considered. Verapamil and diltiazem (non-dihydropyridine calcium channel blockers and moderate inhibitors of CYP3A4) should be used with caution due to a potential CYP3A4 interaction. In general, it is advisable for sites to be prepared, so that antihypertensive medication is readily available in case of need.

In the event of the occurrence of arterial hypertension \geq 150/90 mmHg during infusion of copanlisib at any cycle, antihypertensive treatment is suggested as indicated in Table 9-7. In the event of the occurrence of CTCAE Grade 3 arterial hypertension (\geq 160/100 mmHg) during infusion of copanlisib, the infusion should be interrupted and antihypertensive treatment as suggested above is administered. Infusion can be resumed when blood pressure has returned to $<150/90$ mmHg.

Guidelines for the monitoring and treatment of copanlisib induced hyperglycemia

Hyperglycemia is a common side effect of PI3K and also mTOR inhibitors. Hyperglycemia is often infusion-related and is dose-dependent. Transient increase of glucose levels have been observed in some patients. Regular monitoring of FPG to identify early hyperglycemia and prevent acute/sub-acute complications is important. Caution is warranted for patients with history of DM, or taking corticosteroids, or with other severe medical conditions (e.g. infections), or patients who show potential acute signs such as poly-nocturia, polydipsia, confusion, etc. Hyperglycemia management guidance includes patient education and dietetic measures/life-style changes as well as appropriate anti-diabetic medications as per investigator's decision and/or local guidelines.

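### Table 9-7 and Section 9.8 give different instructions for Grade 3 hypertension during and after copanlisib infusion, and need to be reconciled

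*Combined protocol and SAP*

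**What the plan says.** Two places govern high blood pressure around the copanlisib infusion: the arterial hypertension rows of Table 9-7 (Section 9.7), and two blocks of text in Section 9.8, one on copanlisib-induced arterial hypertension and one on treating blood pressure increases.

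**During infusion, Grade 3 (160/100 mmHg or above).** Table 9-7: "Infusion can be interrupted or slowed down and administration of BP lowering therapy should be initiated". It continues: "Infusion maybe resumed when BP has returned to < 150/90 mmHg at the investigator's discretion or skipped". It then allows later doses to be lowered by one level at the investigator's discretion. Section 9.8 says that, for the same grade, "the infusion should be interrupted and antihypertensive treatment as suggested above is administered", and then: "Infusion can be resumed when blood pressure has returned to" below 150/90 mmHg.

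**After the dose, drug-related Grade 3 not controlled by optimal antihypertensive treatment.** Table 9-7: "Subsequent study drug administrations maybe reduced by 1 dose level". Section 9.8: "the dose for the subsequent copanlisib administrations may be reduced by 1 or 2 dose levels". Both leave the decision to the investigator. Section 9.7 describes a dose reduction as a move to the next lower dose in Table 9-6, and caps reductions at two per drug.

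**During infusion, 150/90 mmHg or above.** Section 9.8 says that for such a rise "during infusion of copanlisib at any cycle, antihypertensive treatment is suggested as indicated in Table 9-7".

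The first of the two Section 9.8 blocks closes by sending the reader to Table 9-7, as if the two agreed. No rule says which prevails.

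**The concern.** The same event, in the same patient, is covered by two sets of permitted actions. An investigator who slows an infusion at 160/100 mmHg is within Table 9-7 and departs from Section 9.8. One who cuts the dose by two levels after persistent post-dose hypertension is within Section 9.8 and departs from Table 9-7.

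These rules will be consulted often. Section 9.1.1 and footnote E of Table 10-1 require blood pressure at mid-infusion, at end of infusion, and 1 and 2 hours later on infusion days.

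At stake is consistent handling of a safety event and a clear standard for what counts as a protocol deviation. For patients on 60 mg, the size of a permitted dose cut is also at stake. The text does not say whether a two-level cut uses one or both of the two permitted reductions.

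**Working it through.** No sample-size, power or error-rate figure is involved, so the check is a comparison of texts, followed by the small amount of arithmetic that the documents allow.

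**Step 1: the texts side by side**

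| Event | Table 9-7 | Section 9.8 |
|---|---|---|
| Grade 3 during infusion: the infusion | may be interrupted or slowed | should be interrupted; slowing not offered |
| Grade 3 during infusion: what follows | may resume below 150/90 mmHg, or skip | may resume below 150/90 mmHg; skipping not offered |
| Grade 3 during infusion: later doses | optional cut of 1 level | nothing stated |
| Post-dose drug-related Grade 3 despite optimal treatment: later doses | optional cut of 1 level | optional cut of 1 or 2 levels |
| 150/90 up to 160/100 mmHg during infusion | no row; the 150/90 row is for pre-dose readings | treatment suggested, with a reference to Table 9-7 |

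In the first four rows the trigger is essentially the same in both places, so these are not two rules for two different events.

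**Step 2: effect on the dose**

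Inputs: the ladder in Table 9-6 is 60, 45, 30 mg. Table 9-7 gives 30 mg as the lowest copanlisib level. The post-dose cut is optional in both texts, so no cut is also permitted.

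- From 60 mg: Table 9-7 permits 60 or 45 mg. Section 9.8 permits 60, 45 or 30 mg. The texts differ by the 30 mg option.
- From 45 mg: one level already reaches 30 mg, and no second level exists. Both texts permit 45 or 30 mg. There is no difference.

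The one-versus-two-level conflict therefore changes the dose only for patients on 60 mg. Under Section 9.7 it also cannot arise in cycle 1 unless a DLT has been counted.

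**Step 3: can the number of patients be stated?**

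Section 11.8 reports drug-related Grade 3 hypertension after infusion in about 42% of copanlisib patients. No numerator is given. The only denominator in that paragraph is 76. If it applies (an assumption), 32/76 = 42.1% would fit.

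Applied to this trial, 0.42 × 33 = 13.9 of the 33 phase II patients and 0.42 × 45 = 18.9 of the maximum 45 treated. Section 3.0 gives 29% for hypertension, grade unstated: 0.29 × 33 = 9.6 and 0.29 × 45 = 13.1.

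None of these products counts patients who meet the conflicting rules:

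- The 42% is for events after infusion, so it says nothing about the during-infusion row.
- It carries no condition that the hypertension persisted under optimal treatment, which both post-dose dose rules require.
- The same paragraph reports antihypertensive treatment given to 8 previously untreated patients and to 7 whose controlled hypertension worsened, 15 in all (15/76 = 19.7% on the same assumption). That counts patients treated, not patients whose hypertension persisted despite treatment.

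The documents give no rate for either qualifying event.

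**The case against.** The best defence is that the texts overlap. Interrupting the infusion satisfies both. For persistent post-dose hypertension, no cut or a one-level cut satisfies both. Section 9.8 itself says that acute rises must be managed patient by patient. Section 9.7 has dose reductions in the expansion phase discussed with the principal investigator, at a single institution, which limits divergent handling. For 150/90 mmHg during infusion, Section 9.8 already supplies the instruction, so the faulty reference leaves no patient without guidance.

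Much of this stands, and it limits the size of the point. It does not remove the conflict. Discretion operates within limits, and the two texts set different limits: slowing and skipping are open under one and not offered by the other, and a two-level cut the reverse. The cross-reference is rightly treated as minor.

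Three stronger readings are tempting, and the documents do not support them:

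- A reader might infer that about 14 of 33 phase II patients would fall under the conflicting rows. As shown in the working, the 42% describes a different and wider event, and it is past experience with copanlisib, not a forecast for this combination.
- A reader might infer that one text leads to a completed infusion and the other to an interrupted one. Both permit interruption, and both permit resumption below 150/90 mmHg.
- A reader might infer an effect on the CR rate or on EFS. A path to EFS exists: Section 9.7 requires discontinuation if the same toxicity recurs at the same or worse severity on a lower dose, and Section 14.2 counts discontinuation for adverse events as an EFS event. But neither hypertension text orders discontinuation for Grade 3, a dose cut is not itself an EFS event, and the documents give nothing from which to link copanlisib exposure to response.

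**Conclusion.** The inconsistency is real and should be corrected. For Grade 3 hypertension during infusion, Table 9-7 and Section 9.8 differ on whether the infusion may be slowed or skipped and on whether later doses may be cut. For persistent drug-related Grade 3 hypertension after the dose, they differ on the largest permitted cut, and the two-level option also sits awkwardly with the one-step definition in Section 9.7. The reference for 150/90 mmHg during infusion is a minor defect.

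The dose consequence is bounded: it is at the investigator's discretion, it concerns only events that persist under optimal treatment, and it is confined to patients on 60 mg. How far it reaches in phase II therefore depends on the dose chosen in phase I. How many patients are affected, and whether CR or EFS would move, cannot be determined from the documents.

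The conclusion rests on the wording of the two places and on the absence of a precedence rule, and needs no assumed event rate.

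**What to change.** Reconcile the two hypertension blocks in Section 9.8 with the arterial hypertension rows of Table 9-7, and both with the definition of a dose reduction in Section 9.7, so that each blood pressure range and time point (pre-dose, during infusion, post-dose) has one instruction. If the reconciled text keeps any cut of more than one level, state how it counts against the limit of two reductions. For 150/90 to 160/100 mmHg during infusion, either give Table 9-7 a matching row or remove the reference to it. Which instruction applies in each case is a decision for the clinical team.

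The cost is protocol wording only, with no added procedures, visits or patients.
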